## Analysis Plan

**17.1.1. ALL TEAEs**

Incidence of TEAEs and of suspected ADRs will be presented by SOC and PT and also broken down further by intensity and causal-relationship to study medication. Non-TEAEs will be summarized separately from TEAEs.

Summaries presented by PT will also be provided for the total number of events, the rate per dosage, and the rate per exposure week. The rate per dosage, where a dosage includes all infusion days within a given treatment visit, will be calculated as:

Total number of events / Total number of dosages received

The rate per exposure week will be calculated as:

Total number of events / Total duration of exposure in weeks

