3.8 Assessments

3.8.1 Assessment Periods

The study consists of a three-week Screening period during which assessments are performed to determine eligibility. Eligible subjects will have Baseline assessments performed, and be randomized at Week 0 (Visit 1). At this time, an initial loading dose of blinded IP will be administered at a dose of 2 g/kg divided over 2 days starting after randomization. Maintenance infusions of blinded IP will be given at doses of 1 g/kg over 1 day every three weeks through Week 36 (Visit 13). Note that the loading dosage is divided over 2 days as standard infusion time; however, extensions to 4 days are allowed for tolerability issues or higher weight, i.e., limit for IGIV-C infusion is no more than 80 g/day (corresponding to 80 kg body weight). Similarly the maintenance dosage is infused in 1 day as standard; however extensions for divided dosage over 2 days are allowed for tolerability issues or higher weight, i.e., limit for IGIV-C infusion is no more than 80 g/day (corresponding to 80 kg body weight).

The IP Run-in consists of the loading infusion and maintenance infusions received prior to Week 9 (Visit 4). After completion of the third maintenance dosage at Visit 4 (Week 9), subjects will begin the protocol-prescribed CS tapering which will continue from Week 9 (Visit 4) through Week 36 (Visit 13) provided that clinical status has not worsened as defined in Section 3.3.3, whilst continuing maintenance IP infusions at 3-week intervals. After

completion of the treatment period, there is a 9-week Safety/Follow-up period through Week 45 (Visit 16).

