Changes in these graded parameters are not considered AEs.

- Weight
- Full vital signs including T, RR, HR, SBP, and DBP
- Clinical laboratory assessments: Hematology, Chemistry (see Section 3.8.3)
- HbA1c
- Blood for IgG (trough)
- Fasting serum glucose (following which subject may eat)
- Quantitative/semi-quantitative binding, blocking, and modulating AChR antibodies
- QMG score
- MG Composite
- MG-QOL 15
- MG-ADL
- WHO-5 Well-Being Index
- AEs (includes clinical observation of signs and symptoms suggestive of any significant disease or condition [e.g., thrombosis, anemia, etc.])
- Concomitant medications
- It is suggested that the investigator consider an increase in CS dose after subjects complete the Week 39 (Visit 14) assessments if considered medically indicated.

• Record CS dose prescribed this visit; review subject's prior adherence; instruct subject to continue to document CS doses taken

STUDY WEEK 42 (VISIT 15)

Subjects must hold their acetylcholinesterase inhibitor (e.g., pyridostigmine) dosage for 12 hours prior to Week 42 (Visit 15) to assure accurate assessment of the OMG score.

Assessments to be performed are the following:

- Full vital signs including T, RR, HR, SBP, and DBP
- QMG score
- MG Composite
- AEs (includes clinical observation of signs and symptoms suggestive of any significant disease or condition [e.g., thrombosis, anemia, etc.])
- Concomitant medications
- It is suggested that the investigator consider an increase in CS dose after subjects complete the Week 39 (Visit 14) assessments if considered medically indicated.
- Record CS dose prescribed this visit; review subject's prior adherence; instruct subject to continue to document CS doses taken

STUDY WEEK 45 (VISIT 16)

Subjects must hold their acetylcholinesterase inhibitor (e.g., pyridostigmine) dosage for 12 hours prior to Week 45 (Visit 16) to assure accurate assessment of the QMG score.

This is the Final Study Visit. Assessments to be performed are the following:

- Full physical exam (excluding breast and genitourinary areas) and waist circumference
- Weight
- Full vital signs including T, RR, HR, SBP, and DBP
- Clinical laboratory assessments: Hematology, Chemistry (see Section 3.8.3)
- QMG score
- MG Composite
- MG-OOL 15
- MG-ADL
- AEs (includes clinical observation of signs and symptoms suggestive of any significant disease or condition [e.g., thrombosis, anemia, etc.])
- Concomitant medications

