5.1.4 Safety Analyses

The safety analysis will be based on safety population.

The safety analyses will be addressed by listing and tabulation of AEs (includes suspected ADRs), vital signs, physical assessments and clinical laboratory tests. Data will be described using descriptive analyses.

Adverse events:

Safety analysis will be primarily focused on a descriptive analysis of suspected ADRs. Safety assessment will be based on the prevalence of suspected ADRs that occurred during the clinical trial.

AEs will be coded and classified using MedDRA terms (system organ class and preferred terms).

AEs will be classified as TEAEs or non-TEAEs depending on the comparison of AE onset date/time with the start date/time of study treatment with the IP. A TEAE will be defined as an AE which occurs between the beginning of the first infusion of IGIV-C and the final visit of the clinical trial. A non-TEAE will be defined as an AE which occurs prior to the first dose of IP. Non-TEAEs and TEAEs will be summarized separately.

All AEs will be summarized by presenting subject incidences and percentages, and they will also be listed by body systems with subject identification codes.

In addition, TEAEs, including suspected ADRs, will be summarized, system organ class, preferred term, causal-relationship, intensity (severity) and seriousness (serious vs.

non-serious) using descriptive statistics. At each level of summarization, a subject will only be counted once per system organ class or preferred term using the most severe or causal relationship AE.

AEs temporally associated with the infusion of the IP (i.e., infusional AEs, including infusional suspected ADRs), will be summarized by presenting infusion/subject incidences and percentage and listed. In addition, the infusion rate in effect at the time of onset of the AE, the time the AE is first reported and the time the AE changes materially in intensity and/or resolves will be also reported and listed.

Subjects with deaths, SAEs, suspected ADRs and AEs leading to premature discontinuation from the study will be listed and presented in a narrative form.

AEs for which the investigator causality assessment is missing or undetermined will be individually listed.

Vital signs:

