## Analysis Plan

date/time of the end of study medication exposure, which is defined as three weeks after the stop date/time of the last dose, given the dosages are administered every three weeks. The treatment phase includes two periods: IP run-in period (from the start date/time of the first dose of study medication to immediately before the start date/time of the Week 9 dose), and CS tapering/IP maintenance period (from the start date/time of the Week 9 dose to the date/time of the end of study medication exposure). Observations and measurements will be considered as in screening phase if they take place before the start date/time of the first dose of study medication, and in follow-up phase if they are after the date/time of the end of study medication exposure.

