## 14.1. DERIVATIONS

Duration of exposure (weeks) = (date of last study medication administration – date of first study medication administration + 21)/7. The addition of 21 days is to take into account total exposure time to the study medication since the dosages are administrated every 3 weeks (Week 0, Week 3, Week 6, Week 9, Week 12, Week 15, Week 18, Week 21, Week 24, Week 27, Week 30, Week 33, and Week 36). Based on this derivation, the minimum exposure for any treated subject is 21 days, or 3 weeks.

In the below derivations, a dosage includes all infusion days within a given treatment visit.

Number of dosage(s) received will be determined directly from entries in the eCRF Study Drug Infusion form.

Dosage (g) = Total volume infused for the indicated dosage (mL) x Concentration of 0.1 (g/mL).

Dosage/body weight (g/kg) = Dosage (g) / Weight (kg), using the most recently available weight for the indicated treatment visit.

Number of infusion days will be determined directly from entries in the eCRF Study Drug Infusion form.

Duration of infusion in minutes will be calculated for each infusion day as: Stop time of infusion – Start time of infusion. Duration of infusion in hours will be calculated as: Duration of infusion in minutes / 60. If the time portion of either start or stop date/time is missing, then the duration will be missing for that infusion.

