**17.1. ADVERSE EVENTS**

Adverse Events (AEs) will be coded using MedDRA central coding dictionary, Version 17.1.

Treatment emergent adverse events (TEAEs) are defined as AEs that started on or after the beginning of the first infusion of study medication and prior to the final study visit.

See Appendix 2 for handling of partial or missing dates/times for AEs. In the case where it is not possible to define an AE as treatment emergent or not, the AE will be classified by the worst case; i.e. treatment emergent.

Listings will include TEAEs and Non-TEAEs. Subjects with deaths, serious adverse events (SAEs), suspected adverse drug reactions (ADRs) and AEs leading to premature discontinuation from the study will be listed.

An overall summary of number of subjects and number of events within categories of interest will be provided as specified in the templates.

Document: CCI

Author: PPD

Version Number:

Version Date:

Final 2.0  
12Apr2019

Template No: CCI

Effective Date: 01Apr2016

Reference: CCI

Copyright © 2009, 2010, 2012, 2016 CCI. All rights reserved.

The contents of this document are confidential and proprietary to CCI. Unauthorized use, disclosure or reproduction is strictly prohibited.

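### The adverse event rate per exposure week counts events up to the final visit (Week 45) but weeks only to 21 days after the last dose (Week 39)

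*SAP*

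**What the plan says.** The rate per exposure week is one of the summaries by preferred term in SAP 17.1.1. Its formula is "Total number of events / Total duration of exposure in weeks".

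- **Events.** SAP 17.1 defines treatment-emergent events as "AEs that started on or after the beginning of the first infusion of study medication and prior to the final study visit". Protocol 5.1.4 uses the same window: "A TEAE will be defined as an AE which occurs between the beginning of the first infusion of IGIV-C and the final visit of the" trial. Protocol 3.8.2.6 says of the Week 45 visit: "This is the Final Study Visit. Assessments to be performed are the following".
- **Weeks.** The only exposure duration that the SAP defines is in 14.1: "Duration of exposure (weeks) = (date of last study medication administration – date of first study medication administration + 21)/7". The same section adds that "the minimum exposure for any treated subject is 21 days, or 3 weeks".
- **Phases.** SAP 6.3 ends the treatment phase at the end of exposure, "which is defined as three weeks after the stop date/time of the last dose", and assigns anything later to a follow-up phase.

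The last infusion is at Week 36. Protocol 3.8.1 describes a follow-up of 9 weeks, counted from that infusion. SAP 6.3 starts follow-up three weeks later, at Week 39, so six of the nine weeks lie outside exposure. I found no text that limits the events in this rate to the exposure period or adds the follow-up weeks to the denominator.

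**The concern.** A rate per unit of time is meaningful only if events and time cover the same window. Here an event that starts between Week 39 and Week 45 enters the numerator, while those weeks are left out of the denominator. The SAP draws the needed line in 6.3 but does not use it in 17.1.1.

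The follow-up weeks also differ in kind from the treatment weeks. Infusions have stopped, and Protocol 3.8.2.6 suggests that investigators consider a higher corticosteroid dose after the Week 39 assessments. Hospitalisations for MG are reported as serious adverse events (Protocol 4.4.7.3), and SAP 16.3.1.7 makes those after Week 39 a separate endpoint. Under 17.1.1 the same events would also be spread over exposure weeks that ended before they began. What is at stake is the absolute size of the reported rates.

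**Working it through.** Visit times are nominal. Inputs: last dose at Week 36 and final visit at Week 45 for completers (Protocol 3.8.2.5 and 3.8.2.6); exposure formula (SAP 14.1); follow-up visits 6 and 9 weeks after the last dose for early stoppers who return (SAP 6.4); 20% discontinuation (Protocol 5.2).

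**1. The plan's own figure.** With first and last dose on the same date, (0 + 21)/7 = 3.0 weeks. This matches the minimum stated in SAP 14.1.

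**2. Completers.** Exposure is (36 × 7 + 21)/7 = 273/7 = 39.0 weeks. Events are counted over 45 weeks. At a constant event rate the result is too high by 45/39 = 1.154.

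Now let the follow-up event rate be r times the on-treatment rate. Against the true on-exposure rate, the factor is (39 + 6r)/39:

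| r (assumed) | Factor |
|---|---|
| 0 | 1.000 |
| 0.25 | 40.5/39 = 1.038 |
| 0.50 | 42/39 = 1.077 |
| 1 | 45/39 = 1.154 |

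**3. Early stoppers, constant event rate.** With the last dose at week w, exposure is w + 3 weeks. The factor depends on how long the subject is observed:

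| Last dose (week) | Exposure (weeks) | Seen to 9 weeks after last dose | Last seen 2 weeks after last dose |
|---|---|---|---|
| 0 | 3 | 9/3 = 3.00 | 2/3 = 0.67 |
| 6 | 9 | 15/9 = 1.67 | 8/9 = 0.89 |
| 18 | 21 | 27/21 = 1.29 | 20/21 = 0.95 |
| 30 | 33 | 39/33 = 1.18 | 32/33 = 0.97 |

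A subject last seen less than three weeks after the last dose is credited with exposure that was not observed, so the factor falls below 1.

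**4. Whole arm.** Take 30 subjects: 24 completers and 6 early stoppers (20%), with last dose between Week 6 and Week 30 and last contact 0 to 9 weeks after it (assumed).

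- High end (last dose Week 6, seen to Week 15): (24 × 45 + 6 × 15)/(24 × 39 + 6 × 9) = 1170/990 = 1.18.
- Low end (last dose Week 30, not seen again): (24 × 45 + 6 × 30)/(24 × 39 + 6 × 33) = 1260/1134 = 1.11.

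Each completer has 6 weeks too few in the denominator. A stopper last seen on the day of the last dose has 3 weeks too many. The two balance when 6(1 − f) = 3f, that is, when a fraction f = 2/3 of the arm stops in that way. At the planned 20%, the net effect is upward.

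**5. Between arms.** Compare 40% with 10% stopping, last dose at Week 6 (assumed).

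- Stoppers seen to Week 15: 40% gives (0.6 × 45 + 0.4 × 15)/(0.6 × 39 + 0.4 × 9) = 33/27 = 1.22. 10% gives (0.9 × 45 + 0.1 × 15)/(0.9 × 39 + 0.1 × 9) = 42/36 = 1.17.
- Stoppers last seen at Week 8: 40% gives (0.6 × 45 + 0.4 × 8)/27 = 30.2/27 = 1.12. 10% gives (0.9 × 45 + 0.1 × 8)/36 = 41.3/36 = 1.15.

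The order reverses with the length of observation.

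**The case against.** The strongest reply is that this is a supplementary, descriptive rate on which no decision rests. SAP 17 plans no statistical comparison of safety data unless otherwise specified. Section 17.1.1 also gives subject incidence, event totals and a rate per dosage, and the listings show study day, so late events can be identified. The sampling error is also far larger than the bias: a term with 5 events has a Poisson standard error of about 1/√5 = 45%. All of this stands, and it is why the point is minor. It does not make the rate correct. The table templates mentioned in SAP 8 are not in the text reviewed, so a restriction there cannot be excluded.

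A second reply is that cutting events off three weeks after the last dose may drop product-related events, given the long half-life that Protocol 3.8.2.6 mentions. That is a fair cost of one of the two repairs below. It is met by tabulating the late events separately, or by choosing the other repair.

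Three stronger readings are tempting, and the documents do not support them:

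- **Every rate is overstated.** The measure is labelled as a rate per exposure week. A term whose events all start within exposure already has the right on-exposure rate (r = 0 in step 2), and a term with no events stays at zero.
- **The bias is worse in the arm with more early stopping.** That needs early stoppers to be followed for the full nine weeks. Protocol 3.11 makes the early discontinuation visit depend on the subject's willingness, and SAP 6.4 speaks conditionally of subjects who return. Step 5 shows that the direction can reverse. The documents also give a single discontinuation figure, not one per arm.
- **The per-dosage rate has the same fault.** Its denominator is a count of dosages, not time, so the argument about windows does not reach it.

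**Conclusion.** The rule is wrong as written, and the consequence is minor. In the rate per exposure week, follow-up-phase events are counted with no matching weeks.

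For completers, terms that also occur in follow-up are overstated by 15% at a constant event rate. The excess is about 4% to 8% if follow-up events occur at 25% to 50% of the on-treatment rate; those fractions are assumptions, since the documents give no event rates. If events became more frequent after treatment stops, the excess could be larger than 15%. Terms without follow-up-phase events are not inflated.

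At arm level, the rate is about 1.11 to 1.18 times the rate per week of full observation. This rests on 20% discontinuation, a constant event rate and the stopping patterns in step 4. The direction and size of any between-arm distortion depend on how long early stoppers are observed, and cannot be stated from the documents.

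**What to change.** In SAP 17.1.1, for the per-exposure-week rate only, add one sentence that takes one of two routes:

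- Count only treatment-emergent events with onset in the treatment phase of SAP 6.3, and report follow-up-phase events separately.
- Keep all treatment-emergent events, divide by weeks from first infusion to each subject's last observation, and relabel the result as a rate per week of observation.

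The first keeps the present meaning of the rate but moves late events to a separate table. It also leaves the small opposite error for subjects last seen less than three weeks after their last dose. The second removes both errors but changes what the rate measures. The per-dosage rate should stay as it is.

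The cost is one sentence and a small programming change. Onset, dosing and visit dates are already collected, so no new data are needed.

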**17.1.1.1. Intensity**

Intensity (severity) is classed as mild/ moderate/ severe (increasing severity). The subject incidence of TEAEs by intensity and the subject incidence of TEAEs and suspected ADRs by maximum intensity will be summarized. The incidence of TEAEs and suspected ADRs will also be presented by SOC/PT; if a subject reports a TEAE more than once within that SOC/PT, the AE with the worst case severity will be included for the relevant SOC/PT.

**17.1.1.2. Causal-Relationship to Study Medication**

Causality to study drug, as indicated by the Investigator, is classed as “unrelated”, “doubtful/unlikely”, “possible”, “probable”, or “definite” (increasing level of relationship). The subject incidence of TEAEs and ADRs by relationship will be summarized. The incidence of TEAEs will also be summarized by relationship; if a subject reports the same AE more than once within that SOC/PT, the AE with the worst case relationship to study medication will be used in the corresponding relationship summaries. AEs classified as “definite”, “probable”, “possible” or “doubtful/unlikely” will be defined as suspected ADRs. ADRs will be presented by SOC and PT. A suspected ADR with a causal relationship of “definite” will be defined as an adverse reaction (AR).

**17.1.2. TEAEs LEADING TO DISCONTINUATION FROM THE STUDY**

TEAEs leading to permanent discontinuation from the study will be identified based on the eCRF response to the question ‘Did subject withdraw from the study as a result of this event?’ TEAEs leading to discontinuation will be presented in a listing.

**17.1.3. SERIOUS ADVERSE EVENTS**

Serious adverse events (SAEs) are those events recorded as “Serious” on the Adverse Events page of the eCRF. A summary of serious TEAEs by SOC and PT will be prepared. A listing will also be presented.

Document: CCI

Author: PPD

Version Number:

Version Date:

Final 2.0  
12Apr2019

Template No: CCI

Effective Date: 01Apr2016

Reference: CCI

Copyright © 2009, 2010, 2012, 2016 CCI. All rights reserved.

The contents of this document are confidential and proprietary to CCI. Unauthorized use, disclosure or reproduction is strictly prohibited.

#### 17.1.4. ADVERSE EVENTS LEADING TO DEATH

AEs leading to Death are those events which are recorded as "Fatal" on the Adverse Events page of the eCRF. AEs leading to death will be presented in a listing.

#### 17.1.5. INFUSIONAL ADVERSE EVENTS

Infusional AEs, including infusional suspected ADRs, are those temporally associated with the infusion of the IP and are defined as TEAEs that occur from the initiation of the IP infusion and within 72 hours following the completion of the infusion of the total dosage of IP. These will be summarized by presenting infusional events and subject incidences and percentage. A corresponding listing will also be presented. In addition, the infusion rate in effect at the time of onset of the AE, the time the AE is first reported, and the time the AE changes materially in intensity and/or resolves will be also reported and listed.

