For any subject, all AEs that occur at any time, between the beginning of the first infusion of IGIV-C and the final visit of the clinical trial, will be considered TEAEs.

AEs occurring during the actual IP infusions (i.e., from the initiation of the IP infusion on the first day to the completion of the total dosage of IP on the last day) and within 72 hours following the completion of the infusion of the total dosage of IP on the last day, regardless of other factors that may impact a possible causal association with product administration, will be defined as infusional AEs (i.e., an AE temporally associated with an infusion of the IP) and labeled infusional TEAEs (a subset of TEAEs).

For AEs that occur during infusions, the infusion rate in effect at the time of onset of the AE, the time of onset of the AE and the time of AE change materially in intensity and/or resolves will be captured.

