### 3.3. CHANGES TO ANALYSIS FROM PROTOCOL

In the protocol, efficacy analyses were to be based on the intent-to-treat (ITT) population, consisting of all subjects who were randomized. In this analysis plan, the primary efficacy analysis population has been changed to the modified intent-to-treat (mITT) population, consisting of all subjects who were randomized and received at least one dose of study medication.

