## Analysis Plan

maintenance dosages (1 g/kg) will be infused in one day with an extension to 2 consecutive days (divided dosages) to account for tolerability and/or weight >80 kg. For both loading and maintenance dosages the limit for blinded IGIV-C infusion is no more than 80 g/day, corresponding to an 80-kg body weight for a 1 g/kg per diem dosage.

In addition, the following variables will be derived and summarized separately for the loading dosage and the maintenance dosages:

On a per-subject basis:

- Number of dosage(s) received

On a per-dosage basis (one dosage/treatment visit may include multiple infusion days):

- Dosage in grams
- Dosage/body weight in g/kg
- Number of infusion days

On a per-infusion basis:

- Duration of infusion in hours

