## 15.1. DERIVATIONS

Treatment compliance will be calculated as the total volume infused divided by the total volume prepared, expressed as a percentage. The total volume prepared and dispensed by the pharmacist is the intended dose volume a subject should be given based on the body weight. This total volume prepared is recorded on the eCRF Study Drug Infusion form.

Infusion compliance will be calculated as the actual number of infusions received divided by the expected number of infusions, expressed as a percentage. Note that the number of days of infusions is a function of investigator choice based on both tolerability and weight. Subjects weighing > 80 kg will need to have infusions divided over more than 1 day as the limit for blinded study drug administration is 80 g/day. However, should a subject weigh more than 80 kg, the investigator may choose to divide the loading dose (2 g/kg) over 3 or 4 days as 3 or 4 daily infusions. For maintenance doses (1 g/kg) every 3 weeks, the choice is 1 or 2 days based on either tolerability or weight, given the mandatory dose limit of no more than 80 g/day. For the purpose of infusion compliance calculation, each loading or maintenance dose is counted as a single dosage. The expected number of dosages during the study is equal to 13 for subjects who complete the study. The total number of expected dosages for those who discontinue early is equal to the number of dosing visits, including completion of loading dose, up to the time of discontinuation. (For example, if a subject discontinues between weeks 6 and 9, the number of expected dosages is 3: one loading dose at Baseline, one maintenance dose at Week 3, and one maintenance dose at Week 6.)

Overall compliance will be calculated as treatment compliance multiplied by infusion compliance.

See calculations below.

- Treatment Compliance (%) to study medication will be calculated as follows:

$$\frac{[\text{Total Actual Volume Infused at 1st IP dose}] + \dots + [\text{Total Actual Volume Infused at last IP dose}]}{[\text{Total Volume Prepared for Infusion at 1st IP dose}] + \dots + [\text{Total Volume Prepared for Infusion at last IP dose}]} \times 100$$

- Infusion Compliance (%) to study medication will be calculated as follows:

$$\frac{[\text{Total Number of Dosages Received During the Study}]}{[\text{Total Number of Expected Dosages During the Study}]} \times 100$$

- Overall Compliance (%) to study medication will be calculated as follows:

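### SAP 17.1.5 replaces the protocol's per-infusion incidence of infusional adverse events with an event count that has no denominator, and SAP 3.3 does not declare the change

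*SAP*

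**What the plan says.** Protocol 5.1.4 states that adverse events temporally associated with the infusion "will be summarized by presenting infusion/subject incidences and percentage and listed". The natural reading is two incidences, one per infusion and one per subject.

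SAP 17.1.5 covers the same events and says "These will be summarized by presenting infusional events and subject incidences and percentage". The subject incidence survives. In place of the infusion incidence there is a number of events, with nothing to divide it by.

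SAP 3.3, the section for changes from the protocol, opens with "In the protocol, efficacy analyses were to be based on the intent-to-treat (ITT) population" and records only the move to the modified intent-to-treat population.

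Two other sections bear on the point. SAP 17.1.1 says "Summaries presented by PT will also be provided for the total number of events, the rate per dosage, and the rate per exposure week" and defines the rate per dosage as "Total number of events / Total number of dosages received"; this is for TEAEs as a whole. SAP 14 says of exposure that "the following variables will be derived and summarized separately for the loading dosage and the maintenance dosages", and the number of dosages received is one of those variables.

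**The concern.** The number of dosages varies widely between subjects. SAP 15.1 states "The expected number of dosages during the study is equal to 13 for subjects who complete the study", while a subject who leaves early may have received only the loading dosage. Protocol 3.3.3 and 3.10 withdraw subjects whose MG worsening does not respond or recurs, so the number of infusions depends on how the disease behaves during the taper, and that may differ between arms. The sample-size assumption of 70% against 30% response makes unequal withdrawal plausible, but the documents give no discontinuation rate by arm.

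An event tied to infusions has more chances to occur in a subject who receives more of them. If placebo subjects leave earlier, placebo shows a lower subject percentage and a lower event count, and the relative infusional burden of IGIV-C is overstated. The opposite pattern would understate it. SAP 17 plans no between-group testing of safety data unless otherwise specified, so the descriptive table is itself the result, and no model behind it corrects for exposure.

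**Working it through.** **Inputs.** A completer receives 1 loading and 12 maintenance dosages (Protocol 2.2, SAP 15.1). Discontinuation is assumed to be in the range of 20% overall, with 60 subjects randomized 1:1 (Protocol 5.2). The documents give no infusional event risk, so the risks below are assumptions: L at the loading dosage and m at each maintenance dosage, constant, independent and identical in both arms.

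**The plan's own figure.** The plan gives no figure for infusional events. The sample-size calculation that supplies the 20% does reproduce: [1.96·√(2·0.5·0.5) + 0.842·√(0.7·0.3 + 0.3·0.7)]² / 0.4² = 23.3, so 24 per group; 24/0.8 = 30 per group, 60 in total.

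**Subject incidence after k maintenance dosages.** I(k) = 1 − (1 − L)(1 − m)^k. With L = 0.30 and m = 0.10:

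- I(12) = 1 − 0.7 × 0.9^12 = 80.2%
- I(6) = 1 − 0.7 × 0.9^6 = 62.8%
- I(4) = 1 − 0.7 × 0.9^4 = 54.1%

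**Gap between arms.** If a share d of one arm leaves after k maintenance dosages and nobody leaves the other arm, the first arm's incidence is lower by d × [I(12) − I(k)].

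| L / m | I(12) | I(6) | I(4) | d = 20%, k = 6 / k = 4 | d = 40%, k = 6 / k = 4 |
|---|---|---|---|---|---|
| 30% / 10% | 80.2% | 62.8% | 54.1% | 3.5 / 5.2 points | 7.0 / 10.5 points |
| 20% / 5% | 56.8% | 41.2% | 34.8% | 3.1 / 4.4 points | 6.2 / 8.8 points |

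The 40% column is the extreme in which the whole planned 20% falls in one arm. If both arms lose the same share at the same times, the gap is zero.

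**Counts and dosage denominators.** Take 30 per arm with L = 0.30 and m = 0.10. In a full arm the expected number of dosages with an event is 30 × 0.30 + 360 × 0.10 = 9 + 36 = 45. If 6 subjects (20%) leave after 6 maintenance dosages, the maintenance dosages number 24 × 12 + 6 × 6 = 324, and the expected number is 9 + 32.4 = 41.4. The count falls although the risk has not changed. Divided by dosages and split by type, the arms agree: 9/30 = 30% at loading in both, and 36/360 = 32.4/324 = 10% at maintenance.

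**Why split by dosage type.** Assume 30% at loading and 5% at maintenance. The pooled rate in a full arm is (0.30 + 12 × 0.05)/13 = 6.9%. If 40% leave after 3 dosages in all, it is (0.6 × 0.90 + 0.4 × 0.40)/(0.6 × 13 + 0.4 × 3) = 0.70/9.0 = 7.8%. A pooled rate therefore tilts upward in the early-leaving arm when loading carries more risk.

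**Can planned outputs supply the measure?** An infusional event rate per dosage can be worked out by hand from the SAP 17.1.5 count and the SAP 14 dosage numbers. The percent of dosages with at least one event cannot, because one dosage may carry several events.

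**The case against.** The strongest reply is that exposure is already handled. SAP 17.1.1 gives a rate per dosage, Protocol 4.4.3 makes infusional events a subset of TEAEs, SAP 14 gives the dosage counts, and SAP 17.1.5 plans a listing. This stands in part, since a crude infusional event rate is recoverable. It does not fill the gap. TEAEs run to the final study visit, including the weeks after the last infusion, whereas infusional events stop 72 hours after a dosage is completed. The incidence by infusion is still not among the planned summaries.

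A second reply is that SAP 8 leaves the content of tables to templates. Those are not among the documents, so they may contain the denominator. The text of 17.1.5 should still say so.

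Third, a dosage percentage is free of exposure bias only under constant risk. Protocol 3.4.3.3 allows slower infusion for tolerability and Protocol 3.5 allows premedication, so risk may fall over time. That is correct: a dosage denominator reduces the bias but does not guarantee its removal.

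A reader might also draw two stronger conclusions that the documents do not support. One is a false difference of 17 to 26 points between arms. Those figures, 80.2 − 62.8 and 80.2 − 54.1, compare single subjects. They would describe arms only if everyone in one arm left early and nobody in the other did. The other is that pooling loading and maintenance makes an early-leaving arm look safer. SAP 17.1.5 states no pooling rule, the protocol asks for no split, and a pooled rate per dosage moves the other way when loading risk is higher.

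**Conclusion.** The mismatch is real: a safety summary specified in the protocol has lost its infusion-level incidence, and the SAP does not declare it. The effect on interpretation is modest and conditional. At the planned 20% discontinuation confined to one arm's share, and under the assumed risks, subject incidence shifts by roughly 3 to 5 points; at 30 per arm, 3.5 points is about one subject (30 × 0.035 = 1.05). It reaches about 7 to 10 points (30% and 10% risks) only if 40% of one arm and none of the other leaves early. All of this rests on assumed, constant and independent risks and on unequal attrition, for which the documents give no figure. No hypothesis test or decision rule depends on the table. The change is still worth making, because the comparison is descriptive and the denominator is already derived.

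**What to change.** In SAP 17.1.5 add, by arm and beside the subject incidence, the number and percent of dosages with at least one infusional TEAE and, separately, with at least one infusional suspected ADR. Use dosages received from SAP 14 as the denominator. A dosage is a sensible unit because the infusional window runs from the start of the first infusion day to 72 hours after the whole dosage is completed; state that choice, since the protocol speaks of infusions.

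Show loading and maintenance dosages separately, as SAP 14 does for exposure. This goes beyond what the protocol asks, but it avoids the pooled-rate tilt and matches a safety objective that names both dosage types.

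List any remaining departure from Protocol 5.1.4 in SAP 3.3. A confidence interval that allows for repeated dosages within a subject is optional.

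The cost is a few lines of SAP text and one extra descriptive table from data already collected. Nothing in dosing or conduct changes.
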